1.0 PROTOCOL SUMMARY

1.1 Schedule of Activities (SoA)

Table 1 Schedule of Activities

Treatment Cycle	Pre-Screening	Screening	Treatment Cycles ^a					End of Treatment
			Cycle 1 ^g	Cycle 2	Cycle 3	Cycle 4	After Cycle 4	
Cycle Day		Day -30 to 0	Day 1 +/- 7 days	Day 1 +/- 7 days	Day 1 +/- 7 days	Day 1 +/- 7 days	Day 1 +/- 7 days	Within 30 days
Administrative Procedures								
Informed Consent		X						
Inclusion/Exclusion Criteria		X						
Demographics and Medical History		X						
Prior and Concomitant Medication Review		X	X	X	X	X	Q1C	X
Olaparib Dispensation			X	X	X	X	Q1C	
Clinical Assessments								
Review Adverse Events			X	X	X	X	Q1C	X
ECOG Performance Status		X	X	X	X	X	Q1C	X
Vital Signs and Weight		X	X	X	X	X	Q1C	X
Physical Examination ^b		X	X	X	X	X	Q1C	X

EKG		X						
Laboratory Assessments								
LOH Assessment	X ^d							
iHRD Analysis/Whole Exome Sequencing		X						
PSA		X	X			X	Q3C	X
Testosterone Level		X						
CBC with Differential		X	X	X	X	X	Q1C	X
Comprehensive Serum Chemistry Panel		X	X	X	X	X	Q1C	X
PT/INR and PTT		X						
Urinalysis		X						
Correlative Studies Blood Collection ^e			X			X		X
Research Biopsy ^e		X						X
Radiographic Assessments ^f		X ⁱ				X	Q3C	

- A. One treatment cycle is equal to 28 days
- B. Full physical exam is required at screening. Subsequent physical exams may be targeted.
- C. Refer to Laboratory Manual for details on correlative blood sample processing.
- D. Pathologic assessment to evaluate LOH score is a pre-screening requirement and will be performed on archival tissue or ctDNA. Sufficient tissue must also be available for whole exome sequencing in order to determine iHRD status.
- E. If archival metastatic tissue previously obtained is already available and suitable for research assessments, another metastatic biopsy will not be mandated. Research biopsy will only occur if considered safe and feasible by the treatment team. CBC with Differential, PT/INR and PTT will only be obtained in the pre-screening period if metastatic biopsy is planned.
- F. Radiographic assessments should include a CT chest/abdomen/pelvis and bone scan. PET/CT or MRI may be used as initial screening assessments.
- G. Assessments done during the screening period do not need to be repeated if within 7 days.
- H. Assessments do not need to be repeated if within 7 days
- I. Radiographic assessments do not need to be repeated if within 8 weeks

1.2 Synopsis

Protocol Title: Olaparib in Prostate Cancer Patients With Evidence of Homologous Recombination Deficiency As Assessed Using an Integrated Genomic Signature

Short Title: Novel Genomic Signature and Olaparib Response

Rationale:

Homologous recombination repair (HRR) is a key pathway involved in resolving double-stranded DNA (dsDNA) breaks. Inactivating mutations in homologous recombination (HR) genes have been associated with improved outcomes to PARP inhibitors (PARPi) in men with mCRPC. Our group has developed an integrated approach to calling HRD signatures (iHRD - integrated Homologous Recombination Deficiency) with the goal of predicting sensitivity to DNA damaging therapeutics such as PARPi. This signature is a multiparametric classification that was defined using 418 patient samples from the Stand Up 2 Cancer (SU2C) repository and was subsequently validated on a set of 139 tumors from our UW rapid autopsy program. Importantly, this assay allows us to identify *11-12% of mCRPC patients who do not have mutations in HR genes but who we would predict to have functional loss of HR and therefore stand to benefit from PARP inhibition.* Based on these observations, we hypothesize that iHRD signature analysis will allow us to identify more men who are likely to benefit from PARP inhibitors, including those (11-12% of mCRPC population) who are otherwise excluded from clinical trials evaluating these agents. We therefore plan to conduct a Phase II study to evaluate the utility of using iHRD signature analysis to select patients for treatment with olaparib.

Objectives and Endpoints:

Primary Objective:

Determine the percent of patients achieving a $\geq 50\%$ reduction in PSA (PSA50 response) following at least 12 weeks of treatment with olaparib 300mg twice daily in men with metastatic castration-resistant prostate cancer (mCRPC) who are iHRD+ and who have progressed on a second generation hormonal agent (e.g. abiraterone or enzalutamide).

Secondary Objectives:

1. Determine the percent of iHRD+ mCRPC patients achieving radiographic response per RECIST 1.1 criteria following treatment with olaparib.
2. Determine the radiographic progression free survival (PFS) in iHRD+ mCRPC patients treated with olaparib.
3. Determine the PSA PFS according to PCWG3 criteria in iHRD+ mCRPC patients treated with olaparib.
4. Determine the overall survival in iHRD+ mCRPC patients treated with olaparib.

5. Assess the incidence and severity of adverse events according to the National Cancer Institute- Common Terminology Criteria for Adverse Events (CTCAE) version 5.0.

Exploratory Objectives:

Correlative work will be conducted to assess differences in clinical outcomes in those with vs. without iHRD positivity. This work will also allow us to further understand the biology underlying these differences. Serial blood samples and metastatic tissue will be obtained at baseline and upon progression. Examples of studies to be conducted may include, but are not limited to:

1. Evaluate for differences in radiographic/PSA response and PFS in patients who are iHRD+ compared to patients who are iHRD-.
2. Evaluate for differences in radiographic/PSA response and PFS by specific HR gene involvement.
3. Compare iHRD signature to other functional methods of predicting HRD including large scale state transition (LST) score and COSMIC signature 3/8 status, Telomeric allelic imbalance (TAI) score.
4. Optimize iHRD signature based on the results of this trial and develop a pipeline for calling iHRD from targeted exome panels.
5. Conduct transcript profiling studies on metastatic tissue.

Primary Endpoint:

Lowest on-treatment PSA, following at least 12 weeks of olaparib in men with mCRPC who are iHRD+

Secondary Endpoints:

The following endpoints will be assessed in men with iHRD+ mCRPC treated with olaparib:

1. Radiographic response rate per RECIST 1.1 criteria
2. Radiographic progression free survival (PFS)
3. PSA PFS according to PCWG3 criteria
4. Overall survival
5. Incidence and severity of adverse events according to the National Cancer Institute- Common Terminology Criteria for Adverse Events (CTCAE) version 5.0.

Study Design

This will be a single arm, Phase II study designed to evaluate the clinical activity of olaparib in mCRPC patients with evidence of HRR deficiency as determined using iHRD signature analysis. Patients will initially be screened for eligibility on the basis of a loss of heterozygosity (LOH) score optimized for UW OncoPlex, a clinical grade targeted sequencing assay. Eligible LOH score positive subjects will then enroll and receive treatment with olaparib 300 mg by mouth twice daily. One treatment cycle will be defined as 28-days, and consist of continuous daily dosing of olaparib. All patients will then undergo germline and somatic whole exome sequencing (WES) to assess iHRD status. Only those found to be iHRD+ will be used for the purpose of assessing the primary endpoint (i.e. best PSA response). Those patients that are LOH score-positive/iHRD-negative will be allowed to continue on treatment, however, and will be used in assessment of exploratory objectives. All patients will continue on androgen deprivation therapy (ADT) (i.e. surgical or medical castration), and should have a two-week washout from their most recent mCRPC therapy and weaned from steroids prior to enrolment.

PSA will be measured on day 1 of every third cycle. Radiographic assessment with bone and CT scans will occur every 12 weeks. The primary endpoint will be lowest on-treatment PSA and primary objective is to determine the PSA50 rate. Patients will be permitted to continue until disease progression by radiographic (per RECIST 1.1), PSA (per PWCG3 criteria) or clinical criteria (e.g. increasing pain), whichever comes first. Prior to completing 3 cycles of treatment, patients should not discontinue treatment for PSA progression alone. Patients will come off study at time of clinical, radiographic, or PSA progression. Secondary objectives will include assessment of radiographic PFS, PSA PFS, overall survival, and adverse events.

1.2.1 Inclusion Criteria

Patients are eligible to be included in the study only if all of the following inclusion criteria and none of the exclusion criteria apply:

1. Capable of giving signed informed consent which includes compliance with the requirements and restrictions listed in the informed consent form (ICF) and in this protocol.
2. Subject must be ≥ 18 years of age at the time of signing the informed consent form.
3. Individuals who have documented histologically confirmed adenocarcinoma of the prostate.
4. Subject must have evidence of castration resistant prostate cancer as evidenced by PSA progression (per Prostate Cancer Working Group 3 [PCWG3] criteria) and a castrate serum testosterone level (i.e. ≤ 50 mg/dL)¹.
5. PSA must be at least 2 ng/mL and rising on two successive measurements at least two weeks apart.
6. At least one lesion (measurable and/or non-measurable) that can be accurately assessed at baseline by CT scan, MRI, or PET and is suitable for repeated assessment.

7. Must have progressed on abiraterone and/or a second generation AR antagonist (i.e. enzalutamide, apalutamide, or darolutamide). If these were given in the hormone sensitive setting, patients must also have progressed on at least one prior approved therapy for CRPC.
8. Must have archival tissue available or be willing to undergo metastatic biopsy in order to perform next-generation DNA sequencing and undergo whole exome sequencing.
9. Patient must have a positive LOH score on prior UW OncoPlex testing
10. Patients must have normal organ and bone marrow function measured within 28 days prior to administration of study treatment as defined below:
 - Hemoglobin ≥ 10.0 g/dL with no blood transfusion in the past 28 days
 - Absolute neutrophil count (ANC) $\geq 1.5 \times 10^9$ /L
 - Platelet count $\geq 100 \times 10^9$ /L
 - Total bilirubin $\leq 1.5 \times$ institutional upper limit of normal (ULN)
 - Aspartate aminotransferase (AST) (Serum Glutamic Oxaloacetic Transaminase (SGOT)) / Alanine aminotransferase (ALT) (Serum Glutamic Pyruvate Transaminase (SGPT)) $\leq 2.5 \times$ institutional upper limit of normal unless liver metastases are present in which case they must be ≤ 5 x ULN
 - Patients must have creatinine clearance estimated of ≥ 51 mL/min using the Cockcroft-Gault equation or based on a 24 hour urine test :

$$\text{Estimated creatinine clearance} = \frac{(140 - \text{age [years]}) \times \text{weight (kg)}}{\text{serum creatinine (mg/dL)} \times 72}$$
11. Eastern Cooperative Oncology Group (ECOG) performance status ≤ 2
12. Patients must have an estimated life expectancy ≥ 16 weeks.
13. Male patients must use a condom during treatment and for 3 months after the last dose of olaparib when having sexual intercourse with a pregnant woman or with a woman of childbearing potential. Female partners of male patients should also use a highly effective form of contraception ([see appendix C for acceptable methods]) if they are of childbearing potential

Exclusion Criteria

1. As judged by the investigator, any evidence of serious and/or unstable pre-existing medical or psychiatric condition which in the investigator's opinion makes it undesirable for the patient to participate in the trial.

2. Other malignancy unless curatively treated with no evidence of disease for ≥ 5 years except: adequately treated non-melanoma skin cancer and non-muscle invasive bladder cancer.
3. Resting ECG indicating uncontrolled, potentially reversible cardiac conditions, as judged by the investigator (e.g., unstable ischemia, uncontrolled symptomatic arrhythmia, congestive heart failure, QTcF prolongation >500 ms, electrolyte disturbances, etc.), or patients with congenital long QT syndrome.
4. Persistent toxicities ($>$ Common Terminology Criteria for Adverse Event (CTCAE) grade 2) caused by previous cancer therapy, excluding alopecia.
5. Patients with myelodysplastic syndrome/acute myeloid leukemia or with features suggestive of MDS/AML.
6. Patients with symptomatic uncontrolled brain metastases. A scan to confirm the absence of brain metastases is not required. The patient can receive a stable dose of corticosteroids before and during the study as long as these were started at least 4 weeks prior to treatment. Patients with spinal cord compression unless considered to have received definitive treatment for this and evidence of clinically stable disease for 28 days.
7. Patients considered a poor medical risk due to a serious, uncontrolled medical disorder, non-malignant systemic disease or active, uncontrolled infection. Examples include, but are not limited to, uncontrolled ventricular arrhythmia, recent (within 3 months) myocardial infarction, uncontrolled major seizure disorder, unstable spinal cord compression, superior vena cava syndrome, extensive interstitial bilateral lung disease on High Resolution Computed Tomography (HRCT) scan or any psychiatric disorder that prohibits obtaining informed consent.
8. Patients unable to swallow orally administered medication and patients with gastrointestinal disorders likely to interfere with absorption of the study medication.
9. Immunocompromised patients, e.g., patients who are known to be serologically positive for human immunodeficiency virus (HIV) and are not receiving active treatment or who have a detectable viral load.
10. Patients with known active hepatitis (i.e. Hepatitis B or C).
 - Active hepatitis B virus (HBV) is defined by a known positive HBV surface antigen (HBsAg) result. Patients with a past or resolved HBV infection (defined as the presence of hepatitis B core antibody and absence of HBsAg) are eligible.
 - Patients positive for hepatitis C virus (HCV) antibody are eligible only if polymerase chain reaction is negative for HCV RNA.
11. Any previous treatment with PARP inhibitor, including Olaparib.

12. Any previous treatment with platinum chemotherapy in the metastatic castration-resistant setting.
13. Patients receiving any systemic chemotherapy or radiotherapy (except for palliative reasons) within 3 weeks prior to study treatment.
14. Concomitant use of known strong CYP3A inhibitors (eg. itraconazole, telithromycin, clarithromycin, protease inhibitors boosted with ritonavir or cobicistat, indinavir, saquinavir, nelfinavir, boceprevir, telaprevir) or moderate CYP3A inhibitors (eg. ciprofloxacin, erythromycin, diltiazem, fluconazole, verapamil). The required washout period prior to starting olaparib is 2 weeks.
15. Concomitant use of known strong (eg. phenobarbital, enzalutamide, phenytoin, rifampicin, rifabutin, rifapentine, carbamazepine, nevirapine and St John's Wort) or moderate CYP3A inducers (eg. bosentan, efavirenz, modafinil). The required washout period prior to starting olaparib is 5 weeks for enzalutamide or phenobarbital and 3 weeks for other agents.
16. Major surgery within 2 weeks of starting study treatment and patients must have recovered from any effects of any major surgery.
17. Previous allogenic bone marrow transplant or double umbilical cord blood transplantation (dUCBT).
18. Patients with a known hypersensitivity to olaparib or any of the excipients of the product.
19. Involvement in the planning and/or conduct of the study.
20. Judgment by the investigator that the patient should not participate in the study if the patient is unlikely to comply with study procedures, restrictions and requirements.

Statistical Methods

Based on the PROFOUND study, we estimate a response rate of 20% (H0) in patients with any HR mutations (e.g. BRCA2, ATM, CDK12, CHEK2, etc).² We will require a 50% (H1) response rate in iHRD positive patients to justify further development of this approach for selecting patients for olaparib treatment. Therefore, assuming we enroll 20 iHRD positive patients, this study would provide 87% power at a one-sided alpha of 0.03 to detect a 50% response rate compared to the null rate of 20%. Given that prior experience has shown that ~75% of patients with a positive LOH score will also have evidence of iHRD positivity, we will enroll a total of 30 patients to identify at least 22 iHRD positive subjects. This should allow for a drop out rate of 10% to ensure that at least 20 iHRD positive subjects are able to reach 12 weeks of treatment for the primary endpoint analysis.

[figure not shown]
The primary objective is to determine the percentage of patients who are iHRD+ that achieve a PSA₅₀ response (i.e. $\geq 50\%$ decline in PSA from baseline). The lowest on treatment PSA will be defined as the lowest value following at least 12 weeks of treatment (i.e. the beginning of Cycle 4). The PSA₅₀ response rate will be calculated along with 90% confidence intervals (CI). PSA changes will be presented as waterfall plots per PCWG3 recommendations. If a patient drops out

of the study prior to assessing best PSA response he will be considered as not having had a PSA50 response. However, an additional study subject will be enrolled to ensure an adequate number of subjects are available to estimate the PSA50 response rate.

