5. STUDY POPULATION

Each patient should meet all of the inclusion criteria and none of the exclusion criteria for this study in order to be assigned to a study intervention. Under no circumstances can there be exceptions to this rule. Patients who do not meet the entry requirements are screen failures, refer to section 5.4.

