5.1 Inclusion criteria

Patients are eligible to be included in the study only if all of the following inclusion criteria and none of the exclusion criteria apply:

1. Capable of giving signed informed consent which includes compliance with the requirements and restrictions listed in the informed consent form (ICF) and in this protocol.
2. Subject must be \geq 18 years of age at the time of signing the informed consent form.
3. Individuals who have documented histologically confirmed adenocarcinoma of the prostate.
4. Subject must have evidence of castration resistant prostate cancer as evidenced by PSA progression (per Prostate Cancer Working Group 3 [PCWG3] criteria) and a castrate serum testosterone level (i.e. \leq 50 mg/dL)¹.
5. PSA must be at least 2 ng/mL and rising on two successive measurements at least two weeks apart.
6. At least one lesion (measurable and/or non-measurable) that can be accurately assessed at baseline by CT scan, MRI, or PET and is suitable for repeated assessment.
7. Must have progressed on abiraterone and/or a second-generation AR antagonist (i.e. enzalutamide, apalutamide, or darolutamide). If these were given in the hormone sensitive setting, patients must also have progressed on at least one prior approved therapy for CRPC.
8. Must have archival tissue available or be willing to undergo metastatic biopsy in order to perform next-generation DNA sequencing and undergo whole exome sequencing.
9. Patient must have a positive LOH score on prior UW OncoPlex testing

10. Patients must have normal organ and bone marrow function measured within 28 days prior to administration of study treatment as defined below:

- Hemoglobin ≥ 10.0 g/dL with no blood transfusion in the past 28 days
- Absolute neutrophil count (ANC) $\geq 1.5 \times 10^9$ /L
- Platelet count $\geq 100 \times 10^9$ /L
- Total bilirubin $\leq 1.5 \times$ institutional upper limit of normal (ULN)
- Aspartate aminotransferase (AST) (Serum Glutamic Oxaloacetic Transaminase (SGOT)) / Alanine aminotransferase (ALT) (Serum Glutamic Pyruvate Transaminase (SGPT)) $\leq 2.5 \times$ institutional upper limit of normal unless liver metastases are present in which case they must be ≤ 5 x ULN
- Patients must have creatinine clearance estimated of ≥ 51 mL/min using the Cockcroft-Gault equation or based on a 24 hour urine test:

$$\text{Estimated creatinine clearance} = \frac{(140 - \text{age [years]}) \times \text{weight (kg)}}{\text{serum creatinine (mg/dL)} \times 72}$$

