5.8.1 Background medication

All patients will be maintained on androgen deprivation therapy (ADT) if they have not had a prior orchiectomy for the duration of the study. Patients may also be receiving osteoclast inhibitors for prevention of skeletal related events and these will be permitted to continue.

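### The numeric castrate testosterone limit in inclusion item 4 is given in mg/dL in both eligibility lists, so the number itself screens out no one

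*Combined protocol and SAP*

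**What the plan says.** Inclusion item 4 appears twice with the same content. Section 1.2.1 (synopsis) asks for a "castrate serum testosterone level (i.e. ≤ 50 mg/dL", and section 5.1 (main body) repeats the number and the unit: "castrate serum testosterone level (i.e. \leq 50 mg/dL". Both cite the PCWG3 recommendations.

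The same item has another limb: "Subject must have evidence of castration resistant prostate cancer as evidenced by PSA progression", judged by PCWG3 criteria. Item 5 requires a rising PSA of at least 2 ng/mL. Item 7 requires progression on abiraterone and/or a second-generation AR antagonist. If those drugs were given in the hormone-sensitive setting, it also requires progression on an approved therapy for castration-resistant disease.

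On background therapy, section 5.8.1 says: "All patients will be maintained on androgen deprivation therapy (ADT) if they have not had a prior orchiectomy for the duration of the study". The Study Design text in section 1.2 and section 4.1 likewise describe castration, surgical or medical, as continuing.

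Section 5 says of the entry criteria: "Under no circumstances can there be exceptions to this rule". The Schedule of Activities (Table 1) lists a testosterone level at screening only and gives no threshold.

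**The concern.** A numeric eligibility limit should separate patients who qualify from those who do not. A testosterone limit in milligrams per decilitre cannot do this, because serum testosterone is present in far smaller amounts. The figure is not background text. It stands in both operative eligibility lists, it is offered as the meaning of castrate, and section 5 allows no exceptions to the criteria. No other section supplies a usable number.

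What is at stake is the objective check of castration at entry. The screening measurement is the only scheduled testosterone reading, and it has no working threshold to be compared with. Someone auditing eligibility against the printed number could not cite any testosterone value as a violation.

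**Working it through.** **Inputs.**
- Limit: 50 mg/dL (sections 1.2.1 and 5.1, item 4).
- Other testosterone limits in the documents: none found.
- Physiological range: not given. Assumed here, deliberately wide: non-castrate values from 100 to 10,000 ng/dL.

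**Conversion.** 1 mg = 1,000,000 ng, so
- 50 mg/dL × 1,000,000 = 50,000,000 ng/dL
- 50,000,000 ng/dL ÷ 100 = 500,000 ng/mL
- 50 mg/dL × 10 = 500 mg/L = 0.5 g/L

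**Ratio of the printed limit to an assumed serum level.**

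| Assumed testosterone (ng/dL) | 50,000,000 ÷ level |
|---|---|
| 100 | 500,000 |
| 1,000 | 50,000 |
| 10,000 | 5,000 |
| 100,000 (implausible, as a stress test) | 500 |

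The conclusion does not depend on where in the range one stands. Even at the stress-test value the limit is 500 times too high to exclude the patient.

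**Is it a one-off misprint on one page?** No. The same unit stands in two separate sections. Within the same lists, item 5 gives PSA in ng/mL and the creatinine clearance formula in item 10 uses mg/dL for serum creatinine. The lists therefore use both kinds of unit, and a unit slip in item 4 is a natural explanation.

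**Does the figure feed the design?** Section 6.8 states 87% power at one-sided alpha 0.03 for 20 iHRD-positive patients, testing 20% against 50%. It states no cut-off count. A rule of at least 8 responders in 20 reproduces both figures:
- P(X ≥ 8 | n = 20, p = 0.2) = 0.032, which rounds to 0.03
- P(X ≥ 8 | n = 20, p = 0.5) = 0.868, which rounds to 87%

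Testosterone is not an input to either, so the design calculation is untouched.

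**The case against.** The strongest reply is that this is a unit slip that experienced staff will recognise, and that it changes little. Most of that stands.

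- The number only explains the word castrate. The text still demands a castrate level, and the no-exceptions rule enforces that word as well as the number.
- Item 4 still requires PSA progression, and items 5 and 7 add further requirements.

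A reader might infer that the whole of item 4 excludes no one. It does not follow: only the numeric limit has lost its function.

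A reader might also infer that a non-castrate man could enter, be castrated on study, and have the resulting PSA fall counted as a PSA50 response in this single-arm trial. The documents do not support that chain. Sections 1.2, 4.1 and 5.8.1 describe androgen deprivation that continues, not deprivation that starts at entry. A man whose PSA is rising on that therapy should not show a 50% fall merely because it goes on. A man never treated hormonally would fail item 7. The chain needs a further event, such as inadequate suppression corrected during the study, and nothing in the documents makes that likely.

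Finally, one might size the error by noting that one patient in 20 moves the PSA50 rate by 5 percentage points (1 ÷ 20). That is true of any single misclassified responder. It says nothing about how often this slip would produce one.

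What the reply does not remove is that the printed number is unusable as a limit, in both places, and that nothing else in the documents replaces it.

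**Conclusion.** The point holds for the numeric limit. As printed it equals 50,000,000 ng/dL, which is 5,000 to 500,000 times any non-castrate level in the assumed range of 100 to 10,000 ng/dL, and it screens out no one. That range is an assumption, but the margin makes the result insensitive to it.

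The factor measures the slip, not its consequence. The remaining entry criteria and the continued-castration requirement keep the practical risk small, and the documents give no basis for putting a figure on bias in PSA50. The point still merits correction, because this is a core eligibility definition in a protocol that forbids exceptions.

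The documents alone cannot settle the intended unit. Appendix E excerpts only the PSA and bone progression definitions from PCWG3 and contains no testosterone limit.

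**What to change.** Check the unit in item 4 against the PCWG3 source that the criterion cites. Correct sections 1.2.1 and 5.1 in the same amendment so that the two lists stay identical. Confirm that any eligibility checklist and the screening form carry the corrected unit; these are not part of the documents, so this is a precaution and not a defect found. If patients have already been enrolled, confirm their recorded screening testosterone against the corrected criterion.

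The cost is one unit changed in two places, plus a short check of forms and any existing screening records. No analysis, sample size or schedule needs to change.
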